2.2. Endpoints

Primary Endpoint

Minimum detectable angle of dorsiflexion and plantar flexion of the ankle.

Secondary Measures and Efficacy Endpoints

1. Time to sway when standing with feet together and eyes closed;
2. Vibratory threshold as measured by Rydel Seiffer graduated tuning fork;
3. Distance walked in a timed walk test;

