3. STUDY DESIGN

This study will be performed in patients with peripheral neuropathy who are walking independently, but have complains of balance problems such as recent falls or difficulty walking and show reduced vibratory and proprioceptive sensation during routine neurologic examination. These patients will be tested for proprioceptive and vibratory threshold at the toes and ankles before, during and after receiving anodal tDCS over sensory and motor cortices, as well as sham stimulation. Patients will be blinded and won't know if they are receiving actual stimulation or sham stimulation. Subjects will be asked to participate in 2 sessions. In one of the sessions, decided randomly, the sham stimulation will be applied and during the other session the real tDCS stimulation will be applied. Similar sets of assessments will be performed before, during and after application of real or sham stimulations.

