4.1. Inclusion Criteria

Subject eligibility should be reviewed and documented by an appropriately qualified member of the investigator's study team before subjects are included in the study.

Subjects must meet all of the following inclusion criteria to be eligible for enrollment into the study:

1. Evidence of a personally signed and dated informed consent document indicating that the subject (or a legal representative) has been informed of all pertinent aspects of the study;
2. Subjects who are willing and able to comply with scheduled visits, and study procedures and are able to read and participate in all study assessments;
3. Subjects with axonal predominantly sensory large-fiber distal symmetric polyneuropathy confirmed with EMG/NCS.
4. Subjects who are walking independently without use of cane or walker.
5. Subjects with impaired proprioception and/or vibration at the toes/ankle on routine neurologic examination.
6. Age older than 18 years;

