8. DATA ANALYSIS/STATISTICAL METHODS

8.1. Sample Size Determination

Based on the review of the literature, a sample size of 15-20 patients often time has been used to investigate the effect of tDCS. We plan to recruit 20 patients in this study.

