8.2. Analysis of Primary and Secondary Endpoints

A repeated measure ANOVA will be used to compare the outcome measures before the stimulation, after the real stimulation and after the Sham stimulation.

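### Section 8.2 names a repeated-measures ANOVA with no rule for patients who lack a session; as usually fitted it drops them, which costs precision and may bias real versus sham in an unknown direction

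*Combined protocol and SAP*

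**What the plan says.** The analysis plan for all endpoints is one sentence in Section 8.2: "A repeated measure ANOVA will be used to compare the outcome measures before the stimulation, after the real stimulation and after the Sham stimulation". The primary endpoint in Section 2.2 is "Minimum detectable angle of dorsiflexion and plantar flexion of the ankle".

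Section 3 sets the visit structure: "Subjects will be asked to participate in 2 sessions", and "In one of the sessions, decided randomly, the sham stimulation will be applied and during the other session the real tDCS stimulation will be applied". It adds: "Similar sets of assessments will be performed before, during and after application of real or sham stimulations". A patient who attends only the first session therefore has before and after values for one condition and nothing for the other.

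Section 8.1 states "We plan to recruit 20 patients in this study" and supports this only by precedent: "a sample size of 15-20 patients often time has been used to investigate the effect of tDCS". It makes no allowance for dropout. Nothing in the document covers withdrawal, missing data, replacement, the analysis set, or assessment after a stimulation that ends early. The nearest text is the eligibility criterion "Subjects who are willing and able to comply with scheduled visits, and study procedures" in Section 4.1, which describes intent at entry and is not a rule for missing values.

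**The concern.** The three conditions in Section 8.2 can be filled only by a patient who completes both sessions. The classical repeated-measures ANOVA works on complete profiles, so a patient with session 1 only is normally deleted together with the values already recorded. The same happens to a patient who attends both sessions but lacks one after-stimulation assessment.

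Two things are at stake. With 20 recruited, each lost patient is 5% of the sample. The analysed set also becomes those who came back. If coming back depends on the first-session result, and does so differently for patients who had real first and patients who had sham first, the real-versus-sham contrast among completers can be shifted.

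**Working it through.** **Inputs.** From the document: 20 patients, two sessions with one condition each, random order, three conditions compared. It gives no alpha, power, effect size, SD, correlation or dropout rate, so the figure of 20 cannot be reproduced by any formula. Assumed below: two-sided alpha 0.05, outcome SD 1 in each condition, correlation ρ between sessions, no period or carryover effect. Signs are coded so that positive favours real stimulation.

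**1. Data lost.** Error degrees of freedom are (n − 1)(3 − 1), which is 38 for n = 20. Let 4 patients miss session 2. A standard repeated-measures ANOVA routine then refuses the data as unbalanced. Values in hand are 20 × 3 − 4 = 56. Deletion leaves 16 × 3 = 48, so 8 collected values are discarded and the error degrees of freedom fall to 15 × 2 = 30.

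**2. Precision.** Let d be the mean real-minus-sham difference divided by its own SD. Power comes from the noncentral t with n − 1 degrees of freedom and noncentrality d√n.

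| Completers | d detectable with 80% power | Power at d = 0.66 |
|---|---|---|
| 20 | 0.66 | 80% |
| 18 | 0.70 | 75% |
| 16 | 0.75 | 69% |
| 14 | 0.81 | 63% |

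Much of this loss is the absent second session itself, which no model recovers. Take 4 of 20 lost at random, 2 per order. The standard errors of the difference are:
- nobody lost: √(2(1 − ρ)/20)
- completers only: √(2(1 − ρ)/16)
- all data by likelihood, ρ known: √(2/[16/(1 − ρ) + 2])

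At ρ = 0.3 these are 0.265, 0.296 and 0.284. At ρ = 0.8 they are 0.141, 0.158 and 0.156. Simulation with ρ estimated (4,000 runs per setting) gave 0.294 for completers against 0.283 for likelihood at ρ = 0.3, and 0.159 against 0.158 at ρ = 0.8. The precision gain is modest at low correlation and negligible at high correlation.

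**3. Bias when only one order leaves selectively.** Assume 10 patients per order. Real-first patients with a worse-than-average after-real value fail to return with probability 0.6.
- Lost: 10 × 0.5 × 0.6 = 3, leaving 7 real-first and 10 sham-first patients.
- Mean shift in the real value among the real-first patients who return: 0.6 × 0.399/0.7 = 0.342 SD, where 0.399 is the standard normal density at 0.
- Shift in their real-minus-sham difference: 0.342(1 − ρ).
- Bias over all completers: (7/17) × 0.342(1 − ρ) = 0.141(1 − ρ).

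This gives 0.10, 0.07, 0.04 and 0.03 SD at ρ = 0.3, 0.5, 0.7 and 0.8. Simulation with a true effect of 0.5 SD gave 0.09, 0.07, 0.05 and 0.03. If only sham-first patients leave by this rule, the sign reverses. If both orders follow it, the two shifts cancel.

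**4. Other leaving patterns.** Large-sample simulation of the completers-only estimate, 10% to 30% leaving overall, ρ = 0.5 and 0.8:

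| Who leaves | Bias (SD) |
|---|---|
| At random | 0 |
| Same poor-result cut-off in both orders, no true effect | 0 |
| Same cut-off in both orders, true effect 0.5 SD | −0.01 to −0.04 |
| Only real-first, on poor change | +0.05 to +0.14 |
| Only sham-first, on poor change | −0.05 to −0.14 |

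**5. Keeping session-1 data.** A mixed-model estimate with the correct covariance had bias within 0.003 SD in every row of step 4. In those runs leaving depended only on observed session-1 values.

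**The case against.** **No exclusion is stated.** A reader might infer that the plan discards incomplete patients. Section 8.2 names a method and says nothing about fitting it. A repeated-measures model fitted by likelihood would keep session-1 data. This stands: deletion is how the named method usually behaves, not something the document prescribes.

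**The bias needs an asymmetry.** A reader might also infer that real versus sham will be overstated because poor responders to real stimulation leave. That requires real-first patients to leave on a poor result while sham-first patients with equally poor results return. Section 3 blinds patients, Section 5 says participants usually cannot tell sham from real, and Section 6.3 describes mild sensations only. These points make an order-specific pattern less likely. They do not exclude it: Section 5 sets the sham current to 0 mA, Section 6.3 lists tingling, fatigue and itching after real stimulation, and a perceived benefit could also bring patients back. Direction and size remain unknown.

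**The effect is small against noise.** The 0.6 leaving probability has no source in the documents. At 0.2 (10 × 0.5 × 0.2 = 1 patient lost) the bias is about 0.03 SD at ρ = 0.3 and 0.01 SD at ρ = 0.8. Even at 0.6, the root mean squared error of completers-only against likelihood was 0.307 against 0.284 at ρ = 0.3, but 0.196 against 0.194 at 0.7 and 0.154 against 0.155 at 0.8. This stands as a limit on the importance of the point.

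**The mixed model is not free.** With ρ estimated and response-dependent leaving in both orders, its sampling SD at ρ = 0.8 was slightly larger than that of completers only (0.176 against 0.170). It also needs a period term and a small-sample method to be a complete replacement. Both are included in the fix.

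**Conclusion.** The point holds in a limited form. The plan names a method that, as usually fitted, excludes patients without both sessions and loses their session-1 values, and it gives no rule for such patients. With 4 of 20 lost, 8 collected values go unused and power at d = 0.66 is 69% instead of 80%, although only part of that can be recovered.

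Bias is possible, not established. It is roughly 0.03 to 0.10 SD with about 3 of 20 lost from one order only, or 6% to 20% of an assumed 0.5 SD effect. Its sign depends on which order leaves. With the same leaving rule in both orders it is near zero, or a slight understatement if there is a true effect. The documents do not support a claim that the real effect will be overstated. Every bias figure rests on assumed leaving patterns, correlations and effect sizes. The change is still worth making before data are seen, because it is cheap and removes a choice that would otherwise be made with the results in view.

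**What to change.** In Section 8.2, replace the ANOVA with a linear mixed model with a patient random effect, fixed effects for condition and session (period), and a small-sample degrees-of-freedom method such as Kenward-Roger. Fit it to every randomised patient with at least one post-stimulation value, and report completers only as a sensitivity analysis. The session term matters because unequal losses stop a session effect from cancelling: with 7 real-first and 10 sham-first completers, (10 − 7)/17 = 18% of any session effect would enter the real-versus-sham difference.

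In Section 3, state that data from a completed session are kept after withdrawal, and that scheduled after-stimulation assessments are still recorded where possible if a stimulation ends early. This concerns data collection only.

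**Cost.** Wording in two sections, with no extra patients or visits. The model takes a little more specification and relies on missing-at-random and a covariance assumption. With complete data balanced by order, the real-versus-sham estimate is unchanged.

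### Section 8.2 puts within-session and between-session differences into one three-level ANOVA and names no error term for real versus sham; the default pooled error would generally be miscalibrated for that comparison

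*Combined protocol and SAP*

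**What the plan says.** Section 3 sets up a two-period crossover: "Subjects will be asked to participate in 2 sessions", and "In one of the sessions, decided randomly, the sham stimulation will be applied and during the other session the real tDCS stimulation will be applied". On measurement it adds: "Similar sets of assessments will be performed before, during and after application of real or sham stimulations". Each patient therefore supplies two baselines, one per session, and two post-stimulation values.

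Section 8.2 applies a single method to every outcome, whether primary or not: "A repeated measure ANOVA will be used to compare the outcome measures before the stimulation, after the real stimulation and after the Sham stimulation". It lists three levels, with one 'before'. It does not say whether that level is the session-1 value, the mean of the two session baselines, or something else. It names no real-versus-sham contrast, error term, sphericity correction, period term or significance level.

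The primary endpoint in section 2.2 is "Minimum detectable angle of dorsiflexion and plantar flexion of the ankle". Section 8.1 states "We plan to recruit 20 patients in this study" and rests that number on precedent.

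**The concern.** A one-way repeated-measures ANOVA on three levels has a single error, the patient-by-condition mean square, with (20 − 1) × (3 − 1) = 38 df. That error suits each pairwise comparison only if the three differences (before−real, before−sham, real−sham) have equal variance, which is sphericity.

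The design works against this. Real−sham always spans two sessions and carries the session-to-session variation twice. A 'before' value shares a session with at least one of the post-stimulation values, so part of that variation cancels. An averaged baseline also has less noise of its own. In both cases the pooled error is too small for real versus sham.

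The opposite can also happen. If patients differ in a before-after shift that is the same in both sessions (practice, fatigue, response to sham), the two comparisons with 'before' become noisier and real−sham does not. The pooled error is then too large, and power is lost.

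At stake are the p-value and confidence interval for the comparison that answers the study question. As written, they depend on a software default and an unstated baseline rule.

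**Working it through.** **Inputs.** From the documents: 20 patients (8.1), two sessions with real in one and sham in the other (3), baselines in both sessions (3), three levels (8.2). The plan gives no error rate to reproduce. Assumed, because the documents do not state them: two-sided 5%; equal variance (set to 1) for a single measurement; within-session correlation w = 0.80 to 0.90; between-session correlation b = 0.60 to 0.80.

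**Variances of the differences.**
- Real−sham: D = 2(1 − b).
- Session-1 baseline: the other two differences have variances 2(1 − w) and 2(1 − b).
- Averaged baseline: each of the other two has variance (1 + b)/2 + 1 − (w + b) = 1.5 − w − 0.5b.

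**Miscalibration.** The pooled error gives every difference the average of the three variances. Let R = D / average. The two-sided 5% critical value on 38 df is 2.024, so the approximate false-positive rate is P(|T38| > 2.024/√R).

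| w / b | Baseline | D | Other two | Average | R | Approx. rate | Simulated |
|---|---|---|---|---|---|---|---|
| 0.80 / 0.80 | session 1 | 0.4 | 0.4, 0.4 | 0.400 | 1.00 | 5.0% | 5.1% |
| 0.80 / 0.70 | session 1 | 0.6 | 0.4, 0.6 | 0.533 | 1.13 | 6.4% | 6.3% |
| 0.90 / 0.60 | session 1 | 0.8 | 0.2, 0.8 | 0.600 | 1.33 | 8.8% | 8.8% |
| 0.80 / 0.80 | averaged | 0.4 | 0.3, 0.3 | 0.333 | 1.20 | 7.2% | 7.3% |
| 0.80 / 0.70 | averaged | 0.6 | 0.35, 0.35 | 0.433 | 1.38 | 9.4% | 9.4% |
| 0.90 / 0.60 | averaged | 0.8 | 0.3, 0.3 | 0.467 | 1.71 | 13.0% | 13.4% |

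The simulated column used 40,000 trials of 20 patients per setting with no real-sham difference. In the last row the pooled standard error is 1/√1.71 = 0.76 of the true one. Keeping both baselines as separate observations behaves much like the session-1 case.

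**Other tests under the same assumptions.**
- Overall F, uncorrected: about 5% to 7%.
- Pooled contrast read only after a significant F: about 2.5% to 7%.
- Real−sham against its own error (paired t, 19 df): 4.8% to 5.2%.

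**Opposite direction.** Take w = b = 0.80 (no session variance) and let patients vary in a shift common to both post-stimulation values. Its variance S is in the same units and is added to each comparison with 'before'.
- Session-1 baseline, S = 0.2: R = 0.4/[(0.4 + 0.6 + 0.6)/3] = 0.75, rate about 2.5%.
- Session-1 baseline, S = 0.4: R = 0.4/[(0.4 + 0.8 + 0.8)/3] = 0.60, rate about 1.3%.
- Averaged baseline, S = 0.2: R = 0.4/[(0.4 + 0.5 + 0.5)/3] = 0.86, rate about 3.5%.
- Averaged baseline, S = 0.4: R = 0.4/[(0.4 + 0.7 + 0.7)/3] = 0.67, rate about 1.8%.

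With session variance present, the two effects offset. At 0.90/0.60 with averaged baselines and S = 0.2, R = 0.8/[(0.8 + 0.5 + 0.5)/3] = 1.33, so the error is again too small.

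**The case against.** The strongest reply is that section 8.2 never says real versus sham will be tested with a pooled error. A reader might infer that the planned p-value is wrong and that the trial runs at a 7% to 13% error rate. The documents do not support that. Paired follow-up comparisons, or a condition-by-time ANOVA on the two sessions, also go under the name of repeated-measures ANOVA and hold about 5%. The one test that 8.2 does name, the overall F, is little affected, and Greenhouse-Geisser repairs it. Reading the contrast only after a significant F removes most of the excess. Rates of 10% or more within the assumed correlations need averaged baselines, a rule the plan does not state. With a session-1 baseline and no session variance, sphericity holds and nothing is inflated.

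All of this stands, and it makes the point conditional. It does not remove it. A condition-by-time ANOVA needs four cells, and 8.2 lists three. A baseline from a separate occasion would keep the contrast at about 5%, but section 3 places a baseline in each session. The overall F does not isolate real versus sham. Contrasts with their own error are the remedy, and 8.2 does not specify them.

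**Conclusion.** The point holds as a gap in specification with a conditional cost. Section 8.2 combines differences of two kinds in one factor and leaves open the error term and the use of the two baselines. If the default pooled error is used for real versus sham, the test is generally miscalibrated, in a direction the plan does not control. The size depends mainly on the baseline rule and on how much patients vary from session to session. It rests on assumed correlations, an assumed 5% two-sided level and an ungated contrast, none of which the documents give. It would be wrong to report the upper figures as the trial's error rate, or to treat the error as always anti-conservative. Settling it before data are seen costs almost nothing, so the change should be made.

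**What to change.** In section 8.2:

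1. Name real versus sham as the primary comparison and state the significance level.
2. Test it with its own error: either the standard error of the 20 within-patient real-minus-sham differences (19 df), or a mixed model with an unstructured within-patient covariance. Do not use the pooled ANOVA mean square for it.
3. Say how each session's own baseline enters, as change from that baseline or as a covariate. The choice matters. The real-sham difference in change has variance 4(1 − w), against 2(1 − b) for post-stimulation values alone. At 0.90/0.60 that is 0.4 against 0.8, so change is better. At 0.80/0.80 it is 0.8 against 0.4, so change is worse. A covariate adapts to either case.
4. Include a period term, since each patient receives the two conditions in a random order.
5. Report the difference with its 95% interval. If the three-level F is kept, label it descriptive and apply Greenhouse-Geisser.

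This needs a few sentences and no new data. The price is fewer error degrees of freedom: 38 falls to 19, and the critical t rises from 2.02 to 2.09. The period term and a baseline covariate each use one more.

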9. QUALITY CONTROL AND QUALITY ASSURANCE

The study site may be subject to review by the Institutional Review Board (IRB). It is important that the investigator and their relevant personnel are available during the monitoring visits and possible audits or inspections and that sufficient time is devoted to the process.

10. DATA HANDLING AND RECORD KEEPING

10.1. Case Report Forms/Electronic Data Record

As used in this protocol, the term CRF should be understood to refer to either a paper form or an electronic data record or both, depending on the data collection method used in this study.

A CRF is required and should be completed for each included subject. The investigator has ultimate responsibility for the collection and reporting of all clinical and safety data entered on the CRFs and any other data collection forms (source documents) and ensuring that they are accurate, authentic/original, attributable, complete, consistent, legible, timely (contemporaneous), enduring and available when required. The CRFs must be signed by the investigator or by an authorized staff member to attest that the data contained on the CRFs is true. Any corrections to entries made in the CRFs, source documents must be dated, initialed and explained (if necessary) and should not obscure the original entry.

10.2. Record Retention

To enable evaluations and/or audits from regulatory authorities, the investigator agrees to keep records, including the identity of all participating subjects (sufficient information to link records), all original signed informed consent documents, copies of all CRFs, safety reporting forms, source documents, and adequate documentation of relevant correspondence (eg, letters, telephone calls reports). The records should be retained by the investigator according to International Conference on Harmonization (ICH), local regulations, or as specified in the Clinical Study Agreement (CSA), whichever is longer.

11. ETHICS

11.1. Institutional Review Board (IRB)

It is the responsibility of the investigator to have prospective approval of the study protocol, protocol amendments, informed consent documents, and other relevant documents, eg, recruitment advertisements, if applicable, from the IRB. All correspondence with the IRB should be retained in the Investigator File.

The only circumstance in which an amendment may be initiated prior to IRB approval is where the change is necessary to eliminate apparent immediate hazards to the subjects. In that event, the investigator must notify the IRB in writing immediately after the implementation.

11.2. Ethical Conduct of the Study

The study will be conducted in accordance with legal and regulatory requirements, as well as the general principles set forth in the International Ethical Guidelines for Biomedical Research Involving Human Subjects (Council for International Organizations of Medical Sciences 2002),

Guidelines for GCP (ICH 1996), and the Declaration of Helsinki (World Medical Association 2008).

In addition, the study will be conducted in accordance with the protocol, the ICH guideline on GCP, and applicable local regulatory requirements and laws.

